**BRACHY-CHOR-001** 

#### 3.4.4 General Considerations for AEs

The Medical Dictionary for Regulatory Activities (MedDRA) version 21.0 (or higher) will be used to code verbatim AE terms and baseline signs and symptoms for summarization into system organ classes (SOCs) and preferred terms (PTs).

### **3.4.4.1 AE** Severity

Adverse events will be categorized and graded by the Investigator using standard terminology for grading the severity (intensity) of the AE. This trial will use the NCI-CTCAE version 4.03 (or higher) five-point scale (Grades 1 to 5) with unique clinical descriptions of severity for each referenced AE. Missing severities will not be imputed.

## 3.4.4.2 AE Causality

The relationship between the occurrence of an AE and the trial treatment will be assessed using the categories "none," "unlikely," "possible," "probable," and "definite." This assessment is applied to each trial product (MVA-BN-Brachyury, FPV-Brachyury, and Radiation) individually. For assessing related AEs in analyses, if the relationship of any of the products is considered possible, probable, or definite, the AE will be considered related to trial treatment. In the event of a missing causality, the AE will be classified as related.

## 3.4.4.3 Serious Adverse Events (SAEs)

Refer to trial protocol Section 8.1.4 for the definition of SAEs in this trial.

#### 3.4.4.4 AEs of Special Interest (AESIs)

Refer to trial protocol Section 8.1.5 for the definition of AESIs in this trial.

## 3.5 Analysis and Presentation Methods

#### 3.5.1 General Presentation Methods

Categorical variables will be summarized using frequencies and percentage of subjects within each category, unless otherwise stated. Continuous variables will be summarized using the following statistics: mean, standard deviation, median, minimum, and maximum. Variables that are log normally distributed will be presented using geometric means and confidence intervals. Percentages will be presented to one decimal place. If a frequency is 0, the percentage will not be presented to draw attention to the non-zero cells of the tables.

For continuous statistics, precision will be based on the precision of the original data points. Means and medians will be presented to the original precision plus one decimal place. Standard deviations will be presented to the original precision plus two decimal places. The minimum and

**BRACHY-CHOR-001** 

maximum will be presented to the precision of the original data. In the event these precision rules result in a precision with more than four decimal places, only 4 decimal places will be presented.

All individual data entered in the eCRF and derived data will be listed as measured in subject--level listings. Tables will be sorted by scheduled visit, as appropriate. Listings will be sorted by subject and visit, as appropriate.

#### 3.5.2 Software

All statistical summaries and analyses of safety and efficacy data will be performed using SAS® version 9.4 or higher (SAS Institute, Cary, NC, USA).

## 3.5.3 Efficacy Analyses

## 3.5.3.1 Efficacy Variables

Refer to efficacy and exploratory endpoints in Section 1.5. Other detailed tumor response information such as measurements of lesion size will be provided in subject-level listings only.

## 3.5.3.2 Response Criteria

### **Primary and Secondary Endpoints**

mRECIST criteria will be used for radiographic assessment of the irradiated tumor(s) (target lesions) only. Non-irradiated tumors (non-target lesions) will not be assessed for the primary endpoint by mRECIST, but clinical decisions based on tumor growth may be made on investigator discretion. Additionally, at investigator discretion, irRC principles can be used for target lesion(s). If a subject has enlargement of their target lesion(s) at the first restaging scan after completion of radiotherapy, they may remain on trial until confirmation of progression on a subsequent scan (at least 4 weeks later). Similarly, any response must also be confirmed with a repeat scan at least 4 weeks later. Progression of a non-target lesion does not result in disease progression by the mRECIST evaluation to be used in this trial. The purpose of the trial is to determine if radiation plus vaccine can shrink the irradiated tumor. In these cases, local interventions may be considered to other non-target lesions (surgery, radiation, or ablation) at the investigator's discretion. Progression of any non-target lesion that requires systemic treatment will result in the subject being taken off trial. If a subject must come off trial due to progression of any non-target lesion prior to meeting the evaluable definition, they may be replaced with another subject to ensure statistical power is maintained for the primary analysis.

In some cases, if more than one lesion can be irradiated, multiple target lesions may be selected. Only those that receive adequate radiotherapy (as defined by radiation requirements for enrollment in the trial protocol) will be considered target lesions for RECIST assessments and primary endpoint analysis.

BRACHY-CHOR-001

All subjects in this trial must be assessed for response to treatment, even if there are major treatment deviations. If a subject has not completed adequate treatment to be evaluated for response to treatment, they should still be assessed, but may be replaced to maintain statistical power. The primary endpoint assessment of ORR anytime within 12 months following completion of radiation will be based on the response to adequate treatment, which will require vaccination and completion of adequate radiotherapy. Progression prior to that point will not be considered treatment failure for purposes of primary endpoint analysis.

## **Exploratory Endpoints**

Standard RECIST 1.1 evaluations based on all available non-irradiated lesion data, and Choi and Volumetric evaluations based on irradiated target lesion data, were to be performed by external radiological reviewers, and the results were to be included in exploratory analyses per the protocol. However, due to constraints with the independent reader evaluations, only a limited number of scans were read, and these analyses will not be performed for the purpose of the final CSR. Further details are in Section 3.5.3.5.

### 3.5.3.3 Primary Efficacy Analysis

The primary efficacy endpoint, ORR (defined as the proportion of subjects with CR or PR) based on best post-treatment tumor assessment of target lesion(s) anytime within 12 months after completion of radiation, will be summarized, and the 90% confidence interval will be computed. Due to the discrete and conservative property of the exact (Clopper-Pearson) confidence limit, the Wilson score confidence limits will be used. The Wilson interval has been shown to have better performance than the Clopper-Pearson interval (Brown, 2001).

The success criteria are based on the point estimate of the EAS. At least one responder must be observed in the first 10 subjects to continue to stage 2. For the final analysis, the null hypothesis that ORR is no more than 5% will be rejected if 4 or more responses are observed in all subjects who are included in the EAS (Section 3.2).

#### 3.5.3.3.1 Additional Analyses of the Primary Efficacy Endpoint

Baseline tumor measurements will be taken during the screening period. Objective tumor responses will be assessed every 3 months starting approximately 14 weeks after radiation therapy. Besides ORR based on the best post-treatment tumor assessment within 12 months after radiation therapy and during the trial, ORR will also be summarized for the EAS by visits with scheduled tumor assessments.

Best post-treatment tumor responses within 12 months after radiation therapy and during the trial by mRECIST will also be summarized for the EAS by location of primary tumor and histologic subtype (refer to subgroups summarized in Section 3.3), and for the FAS as a sensitivity analysis. For sensitivity analyses based on the FAS, subjects without post-treatment tumor assessments will be analyzed as non-responders (regardless of survival status) for OR endpoints.

**BRACHY-CHOR-001** 

The 90% Wilson score confidence intervals will be calculated. The duration of response and tumor measurements will only be provided in subject-level listings.

Percent change from Baseline in target lesion by visits will be plotted for the EAS by different subgroups: best OR, current radiation dose group categories (≤ median current radiation dose in Gray and > median current radiation dose in Gray), baseline disease location, and therapy type (proton therapy and other therapy).

## 3.5.3.4 Secondary Efficacy Analyses

## 3.5.3.4.1 PFS Based on Target Lesion(s)

PFS is defined as the time interval from first vaccination to objective tumor progression based on the mRECIST criteria or death, whichever occurs first. Subjects who do not have disease progression or have not died will be censored at the date when the last tumor assessment determines a lack of target tumor progression. The product-limit Kaplan-Meier curve will summarize PFS graphically. Median survival and 95% confidence intervals will be computed based on the product limit method (Greenwood's formula for the standard error estimate) overall and by subgroups defined in Section 3.3. Progression-free survival rates will be summarized by visit where scheduled tumor assessment is performed, along with their Wilson score confidence intervals.

Primary analyses of PFS will be based on the EAS. PFS rates will also be summarized for the FAS where subjects without post-treatment tumor assessment will be considered to have progressed. Median survival and 95% confidence interval will not be analyzed for the FAS, as these estimates will not differ from those for the EAS because censoring at time 0 is equivalent to excluding these subjects.

Additionally, PFS from current treatment versus PFS from previous treatment will be explored. The ratio of current treatment PFS in days / previous treatment PFS in days for each subject will be calculated. Summary statistics will be presented for EAS. It will also be summarized for EAS by current radiation treatment dose categories: <= median current radiation dose in Gray and > median current radiation dose in Gray. Highest dose of radiation treatment for each subject is used as defining the current radiation treatment dose categories. Subject's most recent previous treatment will be used for the derivation and calculation of PFS from previous treatment. Figures will also be generated to present the ratio by overall and by current treatment radiation dose categories.

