##### **10.4.5.2 Secondary Efficacy Analysis**

The primary analysis population for the secondary endpoints is the evaluable analysis set. Secondary analysis will also be performed on the FAS.

PFS is defined as the time interval from first treatment of MVA-BN-Brachyury to objective tumor progression based on target lesion(s) or death whichever occurs first. Patients who do not have disease progression or have not died will be censored at the date when the last tumor assessment determines a lack of progression. The product-limit Kaplan-Meier curve will summarize PFS graphically. Median survival and their 95% confidence intervals will be computed. Progression-free rates will be summarized by visit where scheduled tumor assessment is performed, along with their Wilson score confidence intervals.

PFS per modified RECIST 1.1 based on the investigator's assessment will be used as one of the two secondary efficacy endpoints. The immune-related radiographic response modification requires a confirmation of progressive disease (PD) at least 4 weeks later with imaging; once confirmed, the date of progression is defined as the first date that the total tumor burden was shown to have increased by at least 20% compared with the nadir.

The BPI-SF will be scored as follows:

- Pain intensity Worst, Least, Average in the last week and pain intensity Right now as recorded in eCRF.
- Composite pain severity score (a mean severity score of the above four pain items)
- Composite pain interference score (a mean of the seven interference items). This will be calculated if at least four of the seven interference items have been completed on a given administration. Otherwise, the pain interference score will be considered missing.

Summaries for BPI-SF will be provided by study period and include continuous summary statistics.

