### 10.5 Response Criteria

RECIST version 1.1 will be used for radiographic assessment. However, at investigator discretion, immune-related radiographic response criteria principles can be used. If a patient has enlargement of his/her target lesion at the first restaging scan after completion of radiotherapy, he/she may remain on trial until confirmation of progression on a subsequent scan (at least 4 weeks later). Similarly, any response must also be confirmed with a repeat scan at least 4 weeks later.

For the primary and secondary RECIST-based endpoints, a modified RECIST 1.1 assessment (based on targeted radiated lesion(s)) will be used. Progression of a non-target lesion does not result in disease progression by the modified RECIST evaluation we will use for this trial. The purpose of the trial is to determine if radiation plus vaccine can shrink the irradiated tumor. In these cases, local interventions may be considered to other non-target lesions (surgery, radiation, or ablation) at the investigator's discretion. If a patient must come off trial due to non-target lesion progression, he/she may be replaced with another patient to ensure statistical power is maintained for the primary analysis.

The primary target lesion (the lesion that is selected prior to initiation of therapy) will be measured by RECIST techniques using a modified RECIST 1.1 (only focused on the target lesion for evaluation of the primary endpoint) at baseline. This lesion will be the target that is irradiated. In some cases, if more than one lesion can be irradiated; multiple target lesions may be selected. Only those that receive adequate radiotherapy will be considered target lesions for RECIST assessment and primary endpoint analysis.

All patients in this trial must be assessed for response to treatment, even if there are major treatment deviations. If a patient has not completed adequate treatment to be evaluated for response to treatment, he/she should still be assessed, but he/she may be replaced to maintain statistical power. The primary endpoint assessment of ORR anytime within 12 months post completion of radiation will be based on the response to adequate treatment, which will require vaccination and completion of adequate radiotherapy. Progression prior to that point will not be considered treatment failure for purposes of primary endpoint analysis.

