Modified Response Evaluation Criteria in Solid Tumors (mRECIST): Standard Response Evaluation Criteria in Solid Tumors (RECIST) Version 1.1 to be used only for radiographic assessment of the irradiated tumor(s) (target lesions). Non-irradiated tumors (non-target lesions) will not be part of the mRECIST assessment. Refer to Section 3.5.3.2 for additional details.

**Response:** Response for the primary analysis will be determined using mRECIST or Immune-Related Response Criteria (irRC), in which only target tumors receiving adequate radiotherapy will be considered for RECIST assessment and primary endpoint analysis. Progression of non-

BRACHY-CHOR-001

target lesions will be assessed as exploratory analyses based on standard RECIST 1.1 for this trial. Refer to Section 3.5.3.2 for additional details.

**Progressive Disease (PD)**: Advancement of disease as defined by target tumor enlargement from nadir using mRECIST or irRC. Progression of non-target lesions will not be considered as disease progression for the primary endpoint analysis of this trial.

**Target Lesions:** Only tumors that are measurable and have received adequate radiotherapy will be considered target lesions for determination of response. All other tumors will be considered non-target lesions.

**Objective Response (OR)**: A subject achieving Complete Response (CR) or Partial Response (PR) per mRECIST or irRC.

Objective Response Rate (ORR): The proportion of subjects meeting the criteria for OR.

**Duration of Response**: From the time that criteria are first met for CR or PR (whichever is first recorded) until the first date that recurrent or progressive disease is objectively documented. The smallest target-tumor measurements on trial (i.e., nadir tumor load) will be used as reference for progressive disease.

**Progression Free Survival (PFS)**: The time interval from the date of first trial vaccination to objective tumor progression, or death from any cause occurring prior to tumor progression. The rate of PFS at a fixed time point is defined as the proportion of subjects who have not experienced objective progression or death from the date of first trial vaccination to the fixed time point of interest.

**Brief Pain Inventory-Short Form (BPI-SF)**: A questionnaire to evaluate the severity of a subject's pain and the impact of this pain on the subject's daily functioning.

02 November, 2021

BRACHY-CHOR-001

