#### **Secondary efficacy endpoints:**

- PFS by mRECIST 1.1 or irRC on target lesion(s)
- Improvement in clinical symptoms measured by the BPI-SF

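### PFS can count an unconfirmed late target-lesion rise as progression in one patient and not in another with the same scans, because confirmation depends on the investigator's choice of criteria

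*SAP*

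**What the plan says.** **Protocol.** Section 10.4.5.2 makes investigator-assessed PFS per modified RECIST 1.1 a secondary endpoint, and adds: "The immune-related radiographic response modification requires a confirmation of progressive disease (PD) at least 4 weeks later with imaging". Once confirmed, progression is dated to the first scan with a rise of at least 20% over nadir. The sentence is not limited to any particular scan. Section 10.5, however, says that "at investigator discretion, immune-related radiographic response criteria principles can be used". It mentions confirmation of progression only for enlargement at the first scan after radiotherapy.

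**SAP.** Section 3.5.3.4.1 scores PFS as follows: "PFS is defined as the time interval from first vaccination to objective tumor progression based on the mRECIST criteria or death". It repeats neither the confirmation rule nor the dating rule. Section 1.5 lists the endpoint as PFS by mRECIST 1.1 or irRC, and the General Definitions describe progressive disease as "Advancement of disease as defined by target tumor enlargement from nadir using mRECIST or irRC". The mRECIST definition refers to section 3.5.3.2, which again makes irRC an investigator option. On progression, that section says only: "If a subject has enlargement of their target lesion(s) at the first restaging scan after completion of radiotherapy, they may remain on trial" (until a later scan confirms it, at least 4 weeks on). Section 4, on changes from planned analyses, does not mention confirmation.

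**Censoring.** SAP 3.4.2 and 3.5.3.4.1 censor at the last assessment showing no progression. SAP 3.4.2 also counts patients without CR or PR who leave early as progressed in the by-time-point rates.

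**The concern.** A PFS event should depend on the patient's scans and one stated rule. Here it can also depend on which criteria the investigator chose, and the documents give no rule for that choice.

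Late unconfirmed rises are foreseen. Protocol 4.2.5 lets a patient stay on trial after first evidence of target-lesion progression until a confirmatory scan, because radiotherapy or immunotherapy can cause swelling. That note is not limited to the first scan. Eight scheduled scans follow week 14 (weeks 26 to 110 after radiation), plus the 30-day follow-up scan.

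The PFS curve, overall and subgroup medians, by-visit rates and the ratio of current to previous PFS all rest on this definition. SAP 3.5.3.5 and 4 drop the standard RECIST, Choi and volumetric analyses. Target-lesion PFS is therefore the only PFS that will be reported, and no second criterion will show how sensitive it is.

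**Working it through.** **1. The plan's own figures.** No target or power is stated for PFS. The stated design figures concern response, and they reproduce (stop at 0/10; reject at 4 or more of 29):
- Early stopping at 5%: 0.95^10 = 0.5987 (stated 60%).
- Expected sample size: 10 + (1 − 0.5987) × 19 = 17.62 (stated 17.6).
- Exact two-stage binomial sum: type I error 0.0468 (stated at most 0.05); power at 20% 0.8011 (stated 80%).

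None of these uses a PFS rule.

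**2. Same scans, two results.** Suppose two patients each have a target sum at least 20% over nadir at week 26 and back below that threshold at week 38.
- Patient A is assessed by mRECIST without irRC. SAP 3.5.3.4.1 gives an event at week 26. Section 3.5.3.2 does not alter this, because week 26 is not the first restaging scan (week 14).
- Patient B is assessed with the immune-related modification. Under Protocol 10.4.5.2 the rise needs confirmation. The week-38 scan, 12 weeks later, does not confirm it, so there is no event.

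Had week 38 confirmed the rise, both would be events dated to week 26. The difference is confined to unconfirmed rises.

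**3. Rise with no later scan.** The Kaplan-Meier status depends on whether an unconfirmed rise counts as an assessment showing no progression, and the SAP does not say. SAP 3.4.2 settles the by-time-point rates for early leavers without CR or PR. It does not settle them for an earlier responder who leaves after a rise.

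**4. Size per patient.** With 29 evaluable patients, one reclassification moves a by-visit rate by 1/29 = 3.4 points. As an assumed example, with 95% Wilson intervals:
- 20/29 progression-free: 69.0% (50.8 to 82.7)
- one reclassified, 19/29: 65.5% (47.3 to 80.1)
- four reclassified, 16/29: 55.2% (37.5 to 71.6)

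**5. How many patients.** This depends on measurement error, which the documents do not give. The illustration below simulates 29 patients with a constant true target sum and independent lognormal error at baseline and every scheduled scan. Progression is a ratio of at least 1.2 to the running nadir. A week-14 rise always needs confirmation. After week 14, confirmation at the next scan is required for 0%, 50% or 100% of patients. The entries are expected false PFS events.

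| Assumed SD | By week 50 (0 / 50 / 100%) | By week 110 (0 / 50 / 100%) |
|---|---|---|
| 3% | 0 / 0 / 0 | 0.01 / 0.00 / 0.00 |
| 4% | 0.15 / 0.08 / 0.01 | 0.6 / 0.3 / 0.03 |
| 5% | 1.1 / 0.6 / 0.1 | 4.0 / 2.2 / 0.5 |
| 7% | 5.7 / 3.6 / 1.4 | 15 / 10 / 4.6 |
| 10% | 13 / 9.3 / 5.4 | 25 / 19 / 14 |

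The result also depends on the true course. At SD 4% without confirmation, linear true growth of 10% by week 110 (below the progression threshold) gives about 6.9 false events by week 110, against about 0.65 when stable. Shrinkage of 10% gives about 0.1.

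**6. Can the last scan confirm?** The follow-up visit is 28 to 32 days after the last dose (Protocol 4.2.3), and treatment-period CT has a window of 1 week either side (Protocol 9.4). The gap from the last-dose scan runs from 28 − 7 = 21 to 32 + 7 = 39 days, so the 30-day scan does not always meet the 4-week minimum.

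**The case against.** The strongest reply is that the SAP follows the protocol. The confirmation sentence in 10.4.5.2 belongs to the immune-related modification, and 10.5 makes that modification optional. The SAP has the same structure, with mRECIST or irRC at the investigator's discretion. With the criterion held fixed, the two documents can give the same status. A SAP also need not reprint every protocol sentence for it to remain in force.

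Much of this stands. A reader might infer that the SAP silently removed a confirmation rule that bound every patient. The documents do not support that, because the protocol has no such universal rule. Nor does the SAP score PFS on mRECIST in isolation, since its mRECIST definition leads to section 3.5.3.2 and the irRC option.

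The open-status cases are also few once the criterion is known: a qualifying rise is an event under mRECIST, and is arguably not yet progression under irRC. What remains is that the criterion is not fixed. The mixture comes from discretion written into both documents, and SAP 3.5.3.4.1 was the place to resolve it for analysis.

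**Conclusion.** The concern holds in limited form and is minor. PFS as planned can mix confirmed and unconfirmed progression according to investigator choice, for rises after the first restaging scan. The effect is 3.4 points on a by-visit rate per reclassified patient, assuming 29 evaluable patients, with corresponding changes in the curve, median and PFS ratio. The number reclassified is unknown and may be nil.

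Two stronger conclusions should not be drawn. First, the simulated counts are neither estimates nor upper bounds. They rest on assumed error and an assumed share of patients needing confirmation, and slow true growth raises them. The 0% and 100% columns do not represent SAP against protocol, because both leave that share to the investigator. Second, the trial's main conclusion is not at risk: PFS is descriptive, with no test or target, and the response endpoint and Simon rule do not use it.

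**What to change.** In SAP 3.5.3.4.1, before the final analysis:

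1. Apply the Protocol 10.4.5.2 rule to every patient and every post-radiation scan. A target-lesion rise of at least 20% over nadir is progression only if confirmed by imaging at least 4 weeks later, and is dated to the first rise. Align SAP 1.5 and the definition of progressive disease, and record in section 4 that investigator discretion no longer determines PFS status.
2. State whether a last rise with no later qualifying scan is an event or censored in the Kaplan-Meier analysis. State its by-time-point status for an earlier responder who leaves. Accept the 30-day scan as confirmation only if it falls at least 28 days after the rise.
3. Report, as a sensitivity analysis, PFS with every rise counted at first occurrence.

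The cost is a few SAP sentences and one extra Kaplan-Meier run. Rises before the last dose visit can be confirmed at the next scheduled scan if the patient is still being scanned; the others fall under item 2. The drawback is that late progression is classified only after its confirming scan. Merely recording the present wording as a change in section 4 would not remove the mixture.

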#### 4.2.5 Withdrawal from Vaccination

Patients will be withdrawn from vaccination if any of the following is true:

- Target lesion disease progression as determined by
  - Radiographic disease progression by standard RECIST 1.1
  - Symptomatic disease progression by symptoms with concurrent evidence of any tumor enlargement
  - NOTE: A patient may continue on trial, at the investigator's discretion, with progression if he/she is eligible for local intervention for a non-target lesion progression
  - NOTE: A patient may remain on trial after initial evidence of target lesion disease progression until a confirmatory scan has been performed due to tumor swelling that can occur with radiotherapy and/or immunotherapy
- Patient withdrawal of consent (must document patient rationale for withdrawal)
- Positive pregnancy test
- Intercurrent illness or medical circumstances. If at any time the constraints of this protocol are detrimental to the patient's health, the patient may be removed from protocol therapy. In this event, the reasons for withdrawal will be documented.
- Adverse events meeting the following criteria: Evidence of any  $\geq$  Grade 3 allergic and  $\geq$  Grade 3 autoimmune reaction(s) attributed to vaccine (**except** Grade 3 endocrine-related immune toxicity or Grade 3 endocrine-related immune toxicity that resolves to Grade  $\leq$  1 clinically within 7 days of initiating supportive therapy); or if  $>$  Grade 2 toxicity attributed to vaccine persists for  $>$  28 days, the patient will not receive further vaccine injections. Patients who come off treatment must be followed on trial until resolution of toxicity and until disease progression.

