#### 4.2.6 Premature Discontinuation

Patients will discontinue the trial if any of the following are true:

- Participant requests to be withdrawn from trial; in this event, the reasons for withdrawal will be documented. If at all possible, the patient should return for the Post Treatment Follow-up Visit.
- A patient who is noncompliant with protocol guidelines may be removed from the trial at the discretion of the principal investigator.
- Disease progression, as described in Removal from Protocol Therapy [Section 4.2.5](#)
- Death.

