## 3.4.2 Data Handling Conventions for Efficacy Analyses

For PFS, if a subject has no date of death and has not progressed by the time of the analysis, the subject will be censored at the last radiologic assessment showing that no progression has occurred.

Subjects who have no record of CR/PR and withdraw early from the trial or are lost to follow-up will be considered as non-responders for the ORR analyses and will be considered to have progression for the by-time-point PFS analyses.

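### Kaplan-Meier PFS censors patients who leave for symptomatic target-lesion progression, so the curve and median are too favourable if such exits occur

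*SAP*

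**What the plan says.** **Event.** SAP 3.5.3.4.1 defines PFS as time from first vaccination to "objective tumor progression based on the mRECIST criteria or death, whichever occurs first". Protocol 10.4.5.2 also requires objective progression of the target lesion(s). It sets the threshold at a 20% increase from nadir, confirmed by imaging at least 4 weeks later.

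**Censoring.** Under SAP 3.5.3.4.1 everyone else "will be censored at the date when the last tumor assessment determines a lack of target tumor progression". SAP 3.4.2 repeats the rule: "the subject will be censored at the last radiologic assessment showing that no progression has occurred". Protocol 10.4.5.2 agrees with both. None of the three makes an exception for the reason a patient left.

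**Exit.** Protocol 4.2.5 lists, as one form of target-lesion disease progression that ends vaccination, "Symptomatic disease progression by symptoms with concurrent evidence of any tumor enlargement". Protocol 4.2.6 then ends trial participation for "Disease progression, as described in Removal from Protocol Therapy". Under 4.2.3 one visit with imaging follows about 30 days after the last dose, and the patient is then off trial.

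**By-visit rates.** For patients with no CR or PR who withdraw early or are lost to follow-up, SAP 3.4.2 says they "will be considered to have progression for the by-time-point PFS analyses". This rule is not applied to the Kaplan-Meier curve or median.

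**The concern.** The withdrawal rule and the endpoint use different definitions of target-lesion progression. Take a patient with new symptoms and 10% growth. The protocol calls this target progression and takes the patient off trial. The SAP sees neither objective progression nor death, so it censors the patient at the last scan without objective progression, which may be the scan that showed the growth.

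Kaplan-Meier assumes that censored patients have the same later risk as those who remain. Here they are selected because the target lesion is growing and causing symptoms. Removing them from the risk set without an event pushes the curve up.

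PFS is one of two secondary efficacy endpoints, and its median and curve will be reported from a single arm of about 29 patients. A reader could not tell how much of the median reflects treatment and how much reflects censored failures. The by-visit rates would show lower PFS for the same people, with no explanation in the SAP.

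**Working it through.** **The plan's own figure.** The documents state no PFS median, event count or power, so there is no PFS figure to reproduce. The only design figures are for ORR. They reproduce exactly (early termination 0.599, expected size 17.62, type I error 0.0468, power 0.801) and do not depend on the PFS rule.

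**Inputs.** From the documents: the event and censoring rules above, scans at 14, 26, 38 and 50 weeks after radiation and every 12 weeks after that, and 29 evaluable patients. Assumed, because the documents give no values: the true median *m*, and the share *q* of failures that leave through symptomatic target progression and are not caught by a later scan.

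**Step 1: constant hazard.** Let λ = ln 2 / *m* be the hazard when symptomatic target progression counts as failure. If a share *q* of failures is censored instead, the hazard that Kaplan-Meier sees is λ(1 − *q*). Then:

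- median under the SAP rule = *m* / (1 − *q*)
- 12-month PFS under the SAP rule = 0.5^[(12/*m*)(1 − *q*)]

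| *q* | Median, *m* = 9 | Median, *m* = 12 | Rise in median | 12-month PFS, *m* = 9 | 12-month PFS, *m* = 12 |
|---|---|---|---|---|---|
| 0 | 9.0 | 12.0 | 0% | 39.7% | 50.0% |
| 10% | 10.0 | 13.3 | 11% | 43.5% | 53.6% |
| 20% | 11.25 | 15.0 | 25% | 47.7% | 57.4% |
| 30% | 12.9 | 17.1 | 43% | 52.4% | 61.6% |

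At *m* = 9 and *q* = 20% the rise is 47.7 − 39.7 = 8.0 points. For scale, the binomial standard error at 39.7% with 29 patients is √(0.397 × 0.603 / 29) = 0.091. The shift is a little under one standard error, but it always goes in the same direction.

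**Step 2: simulation on the scan schedule.** This used 29 patients, 2,000 runs and radiation assumed to end at week 12. Symptomatic patients leave when the target lesion fails, and objective progression would have shown at their next scheduled scan. PFS is read 50 weeks after radiation.

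| True median (weeks) | Exits counted as events | SAP rule, *q* = 10 / 20 / 30% |
|---|---|---|
| 39 | 33% | 37 / 40 / 45% |
| 65 | 52% | 55 / 59 / 62% |

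The rise is 3 to 12 points. For the 39-week case the Kaplan-Meier median is 50, 50 and 62 weeks under the SAP rule, against about 48, 42 and 42 weeks when the exits count. With a 65-week median it is 74, 86 and 98 weeks, against about 74, 74 and 73.

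**Step 3: non-target exits, as a check.** When exits are generated independently of target progression (39-week median), the SAP rule gives 34, 33 and 33% for the same three shares. That is essentially the true 33%, so there is no bias in the target-only curve.

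**The case against.** **Objective progression may still be captured.** Protocol 4.2.5 lets a patient stay until a confirmatory scan, 4.2.3 requires imaging at the 30-day visit, and Appendix 1 asks for efforts to document objective progression after treatment stops. This stands in part. It lowers *q* but does not change how the remaining patients are censored. The sentence in 4.2.5 about following patients until progression sits in the adverse-event bullet, and 4.2.6 ends the trial once progression under 4.2.5 is declared.

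**A conservative display already exists.** The by-visit rates treat early leavers without CR or PR as progressed. That is true and useful, but it corrects neither the curve nor the median.

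**Consequence is limited.** PFS is secondary and descriptive, and it carries no decision rule. The EAS also excludes many early exits. This stands, and it is why the point concerns a sensitivity analysis only.

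**Stronger readings that a reader might infer.**

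- *Non-target exits also bias the curve.* SAP 3.5.3.2 says "Progression of any non-target lesion that requires systemic treatment will result in the subject being taken off trial", and these patients are censored too. But Protocol 10.5 and SAP 3.5.3.2 exclude non-target progression from the endpoint by design. Step 3 shows no bias under independence, and the documents do not show dependence.
- *A cumulative-incidence analysis would expose a flattering curve.* It points the other way. At a 9-month median and a 30% share, 1 − 0.7 × (1 − 0.397) = 57.8%, against a Kaplan-Meier value of 52.4%.
- *The inflated median will be set against the medians in Protocol Table 1.* Neither document plans that comparison. The planned historical comparison is for ORR.

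**Conclusion.** The point holds for symptomatic target-lesion progression. The protocol treats it as progression of the very lesion that PFS measures, yet the Kaplan-Meier analysis censors it, and the direction of the resulting bias is clear. It is confined to the PFS curve and median. The by-visit rates handle these patients conservatively, and the ORR decision is untouched.

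The size cannot be derived from the documents. Under an assumed 10-30% share and constant hazards the median rises by about 11-43%. At a 9-month median, a 20% share adds about 8 points at 12 months. Shares caught by the 30-day scan drop out, and with no such exits the bias is zero. The documents do not support extending the claim to non-target exits.

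**What to change.** In SAP 3.5.3.4.1, keep the primary PFS definition and add:

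1. A Kaplan-Meier sensitivity analysis (curve and median, EAS). The event is the earliest of objective mRECIST progression, investigator-documented symptomatic target-lesion progression under Protocol 4.2.5 (on the documented date), or death.
2. A table of the number censored by reason, with removal for non-target progression needing systemic treatment on its own line.

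No withdrawal or treatment rule changes.

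**Cost.** One extra table and one figure, and a sensitivity PFS that may look less favourable. SAP 3.5.4 already lists discontinuation dates and reasons. The sponsor should check that the recorded reason separates symptomatic from radiographic target progression, because the documents do not say. The SAP introduction labels later additions as unplanned, so this should be written in before the final analysis.
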